1.5.2 Natural History of COVID-19

The incubation period for SARS-CoV-2 is approximately four to five days (range: two to seven days) (46, 47), and most individuals who develop symptoms (~98%) will do so within 11.5 days post-infection (46). Acute manifestations of COVID-19 include the following signs and symptoms: fever, cough, shortness of breath, fatigue, myalgia, nausea/vomiting or diarrhea, headache, rhinorrhea, anosmia, and ageusia. (48).

Many COVID-19 patients present with mild disease (approximately 80%). Although mild, symptomatic COVID-19 often resolves five to seven days (and up to 14 days) after symptom onset, there is growing recognition of the occurrence of postinfectious sequelae lasting for months in individuals, including young, physically fit individuals who initially experienced mild acute illness (49). Fatigue, dyspnea, cough, arthralgia, and chest pain are among the most commonly reported. Based on current available evidence, postinfectious sequelae may also include serious outcomes: cardiac (myocardial inflammation, ventricular dysfunction), respiratory (pulmonary function abnormalities), renal (acute kidney injury), dermatologic (rash, alopecia), neurologic (altered cognition, memory impairment, olfactory and gustatory dysfunction, sleep dysregulation), and psychiatric (depression and changes in mood).

Approximately 20% of patients will progress to more severe COVID-19 characterized by worsening dyspnea and hypoxia, severe pneumonia with >50% lung involvement on imaging. The median time from symptom onset to hospitalization is seven days; range: three to nine days post-symptom onset (50). Five percent of patients progress to critical COVID-19 manifested as acute respiratory distress syndrome, septic shock and/or multiorgan system dysfunction (47, 51, 52, 53). Cardiac, neurologic, hepatic, renal and hematologic complications may occur (54). Mortality in hospitalized COVID-19 patients ranges from 15% to 40% (55).

Reports of reinfection and vaccine breakthrough infections have become more frequent with emerging novel variants, but still remain relatively infrequent, with vaccination post-infection yielding a greater than two-fold reduction in reinfection risk (56).

Anti-SARS-CoV-2 Immunoglobulin Intravenous (Human) (NP-028), abbreviated as COVID-HIG
EBS-CVH-006, Version 3.0, 18 Feb 2022

1.5.3 Current Standard of Care for the Treatment and Prevention of COVID-19

General methods to prevent COVID-19 based on current guidance are to wear a mask in public settings, practice social distancing and avoid crowds and poorly ventilated indoor spaces (57). In December 2020, regulatory agencies in both the US and Canada authorized emergency use of the Moderna® and Pfizer-BioNTech® vaccines for pre-exposure prophylaxis of COVID-19 (58, 59, 60, 61). Although these vaccines are widely available in the U.S. and Canada, as of mid-July 2021, less than 60% of each country's population has been fully vaccinated (62). With emerging variants of increased transmissibility and severity (63), COVID-19 remains an urgent public health threat.

Individuals with mild to moderate COVID-19 disease not requiring supplemental oxygen are currently provided with symptomatic treatment if needed and instructed to follow public health protocols for self-isolation and return to the hospital if symptoms worsen. Several SARS-CoV-2 mAb (casirivimab plus imdevimab, bamlanivimab plus etesevimab or sotrovimab) are available under EUA for outpatients who are at high risk of disease progression and as post-exposure prophylaxis in high risk individuals (casirivimab plus imdevimab and bamlanivimab plus etesevimab) (64, 65, 66). The current standard of care for hospitalized patients with severe disease requiring supplemental oxygen includes dexamethasone with or without remdesivir in addition to supportive care. Current NIH treatment guidelines (updated 15Sep2021) recommend these mAbs for a broad range of high-risk patients ≥ 12 years of age that are likely to progress to more severe disease, however they are not considered SOC for all that test positive for SARS-CoV-2 (67).

1.6 Hypothesis

No statistically-powered hypothesis is tested in this Phase 1 study. It is hypothesized that COVID-HIG in all three routes of administration (IM, SC, and IV) is well-tolerated and that concentrations of SARS-CoV-2 antibodies will be measurable over time, with derived PK parameters in line with immunoglobulin product class kinetics.

2 STUDY OBJECTIVES AND PURPOSE

2.1 Study Purpose

This study is designed to evaluate safety and PK of COVID-HIG administered as IM, SC, or IV routes as a single dose in healthy adults.

Like other human immunoglobulin products, the hyperimmune products manufactured by Emergent (see Section 1.3.1) have been studied in several healthy adult volunteers and clinical studies with patients; the safety profile of these hyperimmune products is consistent with other commercial hyperimmune products and the PK profile is typically similar to the PK of licensed hyperimmune products, with a half-life of approximately 24 to 30 days after IV administration.

Results from this clinical study will provide safety information on intramuscularly and subcutaneously administered COVID-HIG, as well as PK parameters such as peak COVID-HIG plasma levels, trough titers of SARS-CoV-2 antibodies, and COVID-HIG half-life in healthy

Anti-SARS-CoV-2 Immunoglobulin Intravenous (Human) (NP-028), abbreviated as COVID-HIG
EBS-CVH-006, Version 3.0, 18 Feb 2022

adults; the safety data and PK parameters from this study (along with data available from other ongoing or planned clinical studies with COVID-HIG) will be used for dose optimization/dose selection for the proposed COVID-HIG indications (treatment of COVID-19; post-exposure prophylaxis of COVID-19).

2.1.1 Dose Rationale

The proposed dose for this clinical study (approximately 8–16 mg/kg based on an estimated participant weight of 50–100 kg) is within the dose levels tested in clinical studies of other licensed hyperimmune products and is expected to display similar safety and PK profile to those products. The selected dose for this clinical study is \approx 250,000 Alliance Units (AU), based on COVID-HIG product lot potency of 29,282 AU/mL in the wild-type neutralization assay (performed at the NIAID analytical laboratory), resulting in a dose volume of 8.5 mL. The COVID-HIG lot potency is derived using an internal standard that has been established in the NIAID sponsored treatment study INSIGHT-013 (clinical lot potency of COVID-HIG is 29,282 AU/mL). The selected dose is based on antibody titer data available from treatment studies with COVID-19 convalescent plasma (CCP) and SARS-CoV-2 antibody-based therapeutics and vaccine trials as well as emerging literature on protective antibody levels (17, 21, 22, 68, 69, 70). The proposed dose potency is within the range of COVID-HIG doses that have been used for treatment of hospitalized COVID-19 patients (INSIGHT-013; NCT04546581) and for early treatment of high-risk COVID-19 patients (INSIGHT-012; NCT04910269).

As part of Emergent's manufacturing process for COVID-HIG, identification and screening of convalescent plasma donors is performed to select plasma as source material for manufacturing of COVID-HIG from COVID-19 convalescent donors that have been vaccinated against COVID-19. Plasma screening is primarily with an in-house immunobinding assay to SARS-CoV-2 Spike protein, however several assays including viral (wild type and pseudovirus) neutralization and external binding assays including the Ortho VITROS and the Diasorin LIAISON SARS-CoV-2 S1/S2 IgG immunoassays, have been assessed for correlation. This experience has identified a range of neutralizing titers in non-vaccinated convalescent donors, which are typically around 20-50 AU/mL (data on file). Plasma testing data generated by Emergent allow a high-level comparison of COVID-HIG neutralizing antibody potency to that of CCP used in therapeutic clinical trials. COVID-19 convalescent plasma treatment in hospitalized patients from the US National registry demonstrated that higher titers of binding and neutralizing antibodies were associated with decreased 30-day mortality (21). Extrapolating based on our calculations of COVID-HIG and high-titer CCP potency, COVID-HIG is estimated to be at least 60 times as potent as high titer CCP based on the Ortho VITROS assay. Informal comparison of COVID-HIG potency to the high titer CCP in an early treatment study in elderly patients Argentina (22), suggest that COVID-HIG contains approximately 100-fold higher neutralizing antibody levels than CCP. Thus, a dose of 250 mL high titer CCP in the aforementioned study that was associated with a reduction in incidence of severe disease, is expected to be equivalent to approximately 2.5 mL of COVID-HIG.

Vaccine studies also provide an early estimate of antibodies levels that correlate with protection, especially as vaccine studies include results comparing convalescent plasma control samples with samples from vaccinated subjects (69, 70). Antibody levels achieved post-vaccination after

Anti-SARS-CoV-2 Immunoglobulin Intravenous (Human) (NP-028), abbreviated as COVID-HIG
EBS-CVH-006, Version 3.0, 18 Feb 2022

two doses of vaccine are toward the higher high end of the CCP neutralizing antibody range and remain relatively stable for at least 6 months following vaccination.

Based on cumulative considerations presented above, the selected dose of \approx 250,000 AU is expected to provide substantially higher antibody levels than high titer CCP that was used therapeutically in most clinical trials. Although this study will be performed in healthy, uninfected adults for safety and PK analyses, this dose level will inform future dose optimization/dose selection for future COVID-HIG studies.

2.2 Study Objectives

2.2.1 Primary Objective(s)

The following primary objectives will be evaluated:

- To evaluate safety of COVID-HIG administered IM or SC as a single dose
- To evaluate PK of COVID-HIG administered IM or SC as a single dose

2.2.2 Secondary Objective(s)

The following secondary objectives will be evaluated:

- To compare PK of COVID-HIG IM to COVID-HIG IV
- To compare PK of COVID-HIG SC to COVID-HIG IV
- To compare PK of COVID-HIG SC to COVID-HIG IM

2.2.3 Exploratory Objective

The following exploratory objective will be evaluated:

- To evaluate the effects of COVID-HIG in participants that become Severe Acute Respiratory Syndrome Coronavirus 2 (SARS-CoV-2) positive.

3 STUDY DESIGN

3.1 Study Description

This will be a Phase 1, two-center, open-label, randomized study to evaluate one dose level of COVID-HIG administered IM, SC, or IV for safety and PK in healthy adults. Up to 36 adult participants will be targeted to be enrolled in the study. The study has been truncated to 23 randomized participants due to the impact of high circulating SARS-CoV-2 omicron cases on enrollment and participant retention. The sample size with 7-8 participants per study arm will allow for assessment of the primary safety and PK objectives.

Subjects that provide written informed consent and meet eligibility criteria will be stratified based on their SARS-CoV-2 detectable antibody status ($>$ LLOQ, but \leq 80 AU/mL on the Diasorin LIAISON SARS-CoV-2 S1/S2 IgG antibody assay) and undetectable antibody

Anti-SARS-CoV-2 Immunoglobulin Intravenous (Human) (NP-028), abbreviated as COVID-HIG
EBS-CVH-006, Version 3.0, 18 Feb 2022

(\leq LLOQ) at screening, and randomized in two cohorts. If the proportion of subjects in one stratum is high, that stratum may be closed to allow for enrollment in the other stratum.

Table 4 Study Design

Group	Study Arm	No. of Participants	Dosing Schedule – Day 1
Intramuscular	1	Up to 12	\approx 250,000 AU COVID-HIG IM ¹
Subcutaneous	2	Up to 12	\approx 250,000 AU COVID-HIG SC ¹
Intravenous	3	Up to 12	\approx 250,000 AU COVID-HIG IV ¹

¹Exact dose volumes was determined based on the potency of the COVID-HIG clinical lot as defined in Alliance Units (AU) through the wild-type neutralization assay (Clinical lot potency: 29,282 AU/mL, 8.5 mL volume; target protein concentration: 100 mg/mL).

Up to thirty-six participants will be enrolled and assigned equally to one of three study arms to receive a single IM, SC, or IV dose of COVID-HIG, respectively (see the table above). Cohort 1 will consist of 12 subjects; Cohort 2 will comprise up to 24 subjects.

Enrollment into the study will be staggered, wherein no more than three participants will be randomized and dosed on the first day with at least one hour between dosing of each participant. On the second day, up to two more subjects will be randomized and dosed. The remaining participants will be randomized and dosed, with no more than 5 participants dosed per day. Safety data will be reviewed by an SMC (consisting of at least three independent external members) after all 12 participants in Cohort 1 have completed at least 72 hours of safety follow-up. An overall decision by the SMC will be made whether to proceed with full randomization (1:1:1) and dosing of the remaining study participants (Cohort 2, up to n=24).

Participants will be admitted to the inpatient unit one day prior to dosing (Day -1), and following dosing on Day 1, each participant will stay overnight in the inpatient unit for close observation and PK sample collection. Each dosed participant will be discharged from the inpatient unit once all assessments at 24 hours post-dosing timepoint (i.e., Day 2) are completed. Participants will be followed for safety and PK up to 56 days post-dosing (Day 57; see [Table 2](#) for Schedule of Events). Follow-up visits to collect required samples and/or safety assessments can occur in-clinic or at-home as indicated in [Table 2](#).

Study enrollment and administration of study treatments may be paused by the PI or medical monitor for safety review if any of the following occur after study product administration and during the enrollment period:

- One or more SAE(s)
- Three or more of the same AEs classified as Grade 3 severity
- Three or more hypersensitivity AEs classified as Grade 2

AE severity will be graded according to the DAIDS Severity Grading Scale ([Appendix I](#)).

Participants will be followed for 56 days post-dose.

If any participants become positive for SARS-CoV-2 during the study follow-up period, they will be assessed using an Ordinal Outcome Scale ([Appendix II](#)) until symptom resolution and

[figure not shown]
Anti-SARS-CoV-2 Immunoglobulin Intravenous (Human) (NP-028), abbreviated as COVID-HIG
EBS-CVH-006, Version 3.0, 18 Feb 2022

will be followed until they complete their last scheduled follow-up visit (via telemedicine). Participants who test positive for SARS-CoV-2 will be excluded from PK analyses. As such, all subsequent visits should be done via telemedicine following SARS-CoV-2 positive status (except the Day 57 or the withdrawal visit), unless an in-person visit is deemed clinically necessary by the PI. Any in-person visits should be scheduled in a manner that reduces the risks of SARS-CoV-2 transmission, according to local rules and regulations. As the Day 57 or withdrawal visit necessitates in-person safety assessments, this visit should proceed in-person, if possible. If a participant tests positive for SARS-CoV-2 immediately prior to or at the in-person Day 57 visit, reasonable efforts will be made to collect as many of the required samples from the Day 57 visit in a manner that reduces the risk of SARS-CoV-2 transmission, according to local rules and regulations.

For details on schedule of events, refer to [Table 2](#) Schedule of Events.

3.1.1 Schematic Diagram of Study Design, Procedures, and Stages

Figure 1 Schematic of Study Design and Procedures.

3.1.2 Study Center(s)

This study will be conducted at two centers in the US.

Anti-SARS-CoV-2 Immunoglobulin Intravenous (Human) (NP-028), abbreviated as COVID-HIG
EBS-CVH-006, Version 3.0, 18 Feb 2022

3.2 Study Endpoints

3.2.1 Pharmacokinetic Endpoints

3.2.1.1 Primary Pharmacokinetic Endpoints

The following primary PK endpoints (based on PK sample test results of an immunobinding IgG assay) will be evaluated in healthy adults belonging to both strata, detectable SARS-CoV-2 antibody and undetectable antibody (\leq LLOQ) at screening:

- $AUC_{0-\text{inf}}$: $AUC_{0-\text{last}}$ plus the additional area extrapolated to infinity after dosing.
- $AUC_{0-\text{last}}$: area under the concentration-time curve from time 0 to the last quantifiable concentration after dosing.
- C_{max} : maximum observed concentration after dosing.
- T_{max} : time at which C_{max} occurs after dosing.
- $C_{28\text{d}}$: observed or estimated concentration at 28 days after dosing.

3.2.1.2 Secondary Pharmacokinetic Endpoints

The following additional COVID-HIG PK endpoints (based on PK sample test results by an immunobinding IgG assay) will be calculated when data permit:

- $AUC_{0-\text{inf}}$ ratios (bioavailability) will be compared between routes for comparable dose levels (COVID-HIG SC to IV; IM to IV; and SC to IM).
- $AUC_{0-14\text{d}}$ after dosing.
- $AUC_{0-28\text{d}}$ after dosing.
- λ_z : terminal elimination rate constant after dosing.
- $T_{1/2}$: apparent terminal elimination half-life after dosing.
- CL : systemic clearance after dosing.
- V_z : volume of distribution after dosing.

3.2.2 Exploratory Endpoints

Descriptive analyses of COVID-19 disease severity among SARS-CoV-2 positive subjects as assessed by an Ordinal Outcomes scale ([Appendix II](#)).

3.2.3 Safety Endpoints

3.2.3.1 Primary Safety Endpoints

The following primary safety endpoints will be evaluated:

- AEs within 72 hours post-dosing.

Anti-SARS-CoV-2 Immunoglobulin Intravenous (Human) (NP-028), abbreviated as COVID-HIG
EBS-CVH-006, Version 3.0, 18 Feb 2022

- AEs and SAEs in healthy adults up to 56 days post- administration of a single COVID-HIG dose.

3.3 Measures Taken to Minimize/Avoid Bias

3.3.1 Masking/Blinding Procedures

As this is an open label study, no masking/blinding procedures are necessary.

3.3.2 Treatment Assignment/Randomization

Enrollment into the study will be staggered. In the sentinel Cohort 1 a total of 12 participants will be randomized 1:1:1 to each study arm. As part of the sentinel cohort, the first three participants will be randomized and dosed on the first day with at least one hour between dosing of each participant. Another nine participants will then be randomized and dosed at least 24 hours after the first three participants have been dosed, with no more than 5 participants dosed per day in this set. Following randomization/dosing of the first four participants in each of the three arms (Cohort 1, n=12), safety data will be reviewed by the SMC once these 12 participants have completed at least 72 hours of safety follow-up. An overall decision by the SMC will be made whether to proceed with full randomization (1:1:1) and dosing of the remaining study participants (Cohort 2, up to n=24). Due to the impact of the COVID-19 pandemic surge in cases affecting enrollment and participant retention, the study has been truncated to 23 participants randomized, with 7-8 participants per study arm.

Subjects will be stratified based on their SARS-CoV-2 detectable antibody status (>LLOQ, but ≤ 80 AU/mL on the Diasorin LIAISON SARS-CoV-2 S1/S2 IgG antibody assay) and undetectable antibody (\leq LLOQ) at screening. If the proportion of subjects in one stratum is high, that stratum may be closed to allow for enrollment in the other stratum.

Randomization lists will be generated by a Randomization and Trial Supply Management (RTSM) system vendor. Details on the randomization procedures will be provided in the Pharmacy Manual. Sites will not be permitted to view the randomization list, and subjects will be assigned to treatment arm according to their stratum and randomization order.

3.4 Description of Stopping Rules

As described in Section 3.3.2, the SMC will evaluate safety data for sentinel participants to determine if the study can proceed to enroll remaining participants. The following related safety stopping rules apply throughout the entire study and will be managed by the SMC:

Study enrollment and IP administration will be temporarily held by the Sponsor if any of the following occur, pending further evaluation:

- One or more SAE(s).
- Three or more of the same AEs classified as grade 3 severity.
- Three or more hypersensitivity AEs classified as grade 2 severity.

Anti-SARS-CoV-2 Immunoglobulin Intravenous (Human) (NP-028), abbreviated as COVID-HIG
EBS-CVH-006, Version 3.0, 18 Feb 2022

These events will be reviewed by the SMC and a recommendation will be made regarding IP administration, continuation of study, or study termination. The procedures for SMC notification and review of AEs will be outlined in the SMC Charter.

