Up to thirty-six participants will be enrolled and assigned equally to one of three study arms to receive a single IM, SC, or IV dose of COVID-HIG, respectively (see the table above). Randomization will be separate for Cohort 1 (12 subjects) and Cohort 2 (up to 24 subjects), but both randomization ratios will be 1:1:1 for each administration route. Subjects will be stratified based on their SARS-CoV-2 detectable antibody status (>LLOQ, but ≤80 AU/mL on the Diasorin LIAISON SARS-CoV-2 S1/S2 IgG assay) and undetectable antibody (≤LLOQ) at screening.

Enrollment into the study will be staggered, wherein no more than three participants will be randomized and dosed on the first day with at least one hour between dosing of each participant. On the second day, up to two more subjects will be randomized and dosed. The remaining participants will be randomized and dosed, with no more than 5 participants dosed per day. Safety data will be reviewed by a Safety Monitoring Committee (SMC) (consisting of at least three independent external members) after all 12 participants in Cohort 1 have completed at least 72 hours of safety follow-up. An overall decision by the SMC will be made whether to proceed with full randomization (1:1:1) and dosing of the remaining study participants (Cohort 2, up to n=24).

Participants will be admitted to the inpatient unit one day prior to dosing (Day -1), and following dosing on Day 1, each participant will stay overnight in the inpatient unit for close observation and PK sample collection. Each dosed participant will be discharged from the inpatient unit once all assessments at the 24 hours post-dosing timepoint (i.e., Day 2) are completed. Participants will be followed for safety and PK up to 56 days post-dosing (Day 57; see [Table 2](#) for Schedule of Events). Follow-up visits to collect required samples and/or safety assessments can occur in-clinic or at-home as indicated in [Table 2](#).

Anti-SARS-CoV-2 Immunoglobulin Intravenous (Human) (NP-028), abbreviated as COVID-HIG
EBS-CVH-006, Version 3.0, 18 Feb 2022

Study enrollment and administration of study treatments may be paused by the PI or medical monitor for safety review by the SMC if any of the following occur after study product administration and during the enrollment period:

- One or more serious adverse event(s) [SAE(s)].
- Three or more of the same Grade 3 adverse events (AEs)
- Three or more Grade 2 hypersensitivity AEs

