4.3.2 Discontinuation of Intervention

If applicable based on randomized route of administration, the injection(s) can be stopped if Grade 2 or higher or serious AE (anaphylaxis or hypersensitivity reaction) are observed. All participants should still be followed-up for the duration of the study for safety. Refer to Section [5.1.4](#) for further information related to AEs and administration of IP.

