8.5 Safety Data Monitoring

An independent SMC will provide on-going review of safety data during the study. In fulfilling these responsibilities, the SMC may make recommendations concerning continuation and/or stopping of the study as it relates to safety and risk to the participant population as outlined in the SMC Charter.

Study enrollment and IP administration may be temporarily paused at the discretion of the PI or MM for safety review by the SMC if any of the following AEs occur after administration of COVID-HIG:

- \geq one SAE regardless of relatedness to IP
- \geq three of the same AEs classified as Grade 3 severity
- \geq three Grade 2 hypersensitivity AEs

These events will be reviewed by the SMC. The procedures for SMC notification and review of safety data will be outlined in the SMC Charter.

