Participants were admitted to the inpatient unit one day prior to dosing (Day -1), and following dosing on Day 1, each participant stayed overnight in the inpatient unit for close observation and PK sample collection. Each dosed participant was discharged from the inpatient unit once all assessments at 24 hours post-dosing timepoint (i.e., Day 2) were completed. Participants were to be followed for safety and PK up to 84 days post-dosing (Day 85) via in-clinic or at-home visits; however, the length of the study was shortened to 56 days (Day 57) in Protocol Amendment 3.0.

Study enrollment and administration of study treatments was to have been paused by the Principal Investigator (PI) or medical monitor for safety review if any of the following occurred after study product administration and during the enrollment period:

- One or more serious adverse events (SAE)
- Three or more of the same adverse event (AE) classified as Grade 3 severity
- Three or more hypersensitivity AEs classified as Grade 2

AE severity is graded according to the Division of Acquired Immunodeficiency Syndrome (DAIDS) Severity Grading Scale per protocol [Appendix I I](#) (DAIDS, 2017).

If any participants became positive for SARS-CoV-2 during the study follow-up period, they were to be assessed using an Ordinal Outcome Scale (see protocol [Appendix II](#)) until they completed their last follow-up visit via telemedicine. Participants who tested positive for SARS-CoV-2 were excluded from PK analysis time points occurring after their positive test. For details of Schedule of Events, refer to [Table 2](#).

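### For the same triggers, the safety pause is a mandatory sponsor hold in protocol 3.4 but an optional pause by the PI or medical monitor in the synopsis, 3.1 and 8.5

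*Protocol*

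**What the plan says.** The pause rule is stated five times, always with the same three triggers: one or more SAEs, three or more of the same Grade 3 AE, or three or more Grade 2 hypersensitivity AEs.

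- **Protocol 3.4 (Description of Stopping Rules):** "Study enrollment and IP administration will be temporarily held by the Sponsor if any of the following occur, pending further evaluation". On scope and ownership it adds that the "safety stopping rules apply throughout the entire study and will be managed by the SMC". The SMC then reviews the events and makes a recommendation on dosing, continuation or termination.
- **Protocol synopsis:** "Study enrollment and administration of study treatments may be paused by the PI or medical monitor for safety review by the SMC", for events after dosing and within the enrolment period.
- **Protocol 3.1 (Study Description):** enrolment and dosing "may be paused by the PI or medical monitor for safety review if any of the following occur after study product administration", again within the enrolment period. The SMC is not named as the reviewer.
- **Protocol 8.5 (Safety Data Monitoring):** enrolment and dosing "may be temporarily paused at the discretion of the PI or MM for safety review by the SMC". No enrolment-period limit is given.
- **SAP 2.2 (Study Design and Conduct):** enrolment and dosing "was to have been paused by the Principal Investigator (PI) or medical monitor for safety review", within the enrolment period.

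**The concern.** The five statements agree on what sets off the rule and disagree on what follows. Section 3.4 leaves no choice and names the Sponsor. The synopsis, 3.1 and 8.5 leave a choice and name the PI or medical monitor. SAP 2.2 has the force of 3.4 and the actors of the other sections.

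Two things are at stake. During dosing, staff at two sites and the sponsor could read the protocol correctly and still reach different conclusions about whether the next participant may be dosed. At reporting, protocol 10.7 defines a deviation as a departure from the procedures that the protocol lays down. Whether not pausing was such a departure depends on which section is used as the standard.

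**Working it through.** The rule has no stated operating characteristic, so there is no plan figure to reproduce. The check is a comparison of the texts, followed by an illustration of how likely the most sensitive trigger is.

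**Step 1. The statements side by side**

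| Place | Force | Who acts | Period | SMC review of the event |
|---|---|---|---|---|
| Protocol 3.4 | Required | Sponsor places the hold; SMC manages the rules | Whole study | Yes, with a recommendation |
| Synopsis | Optional | PI or medical monitor | Enrolment period | Yes |
| Protocol 3.1 | Optional | PI or medical monitor | Enrolment period | SMC not named |
| Protocol 8.5 | Optional, discretion explicit | PI or medical monitor | No limit stated | Yes |
| SAP 2.2 | Reads as required | PI or medical monitor | Enrolment period | SMC not named |

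**Step 2. One SAE while enrolment is open.** Under 3.4 the Sponsor must hold enrolment and dosing. Under the synopsis, 3.1 and 8.5, the PI and medical monitor may decide not to pause. Continued dosing complies with those three and conflicts with 3.4.

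**Step 3. One SAE after the last participant is dosed.** Each participant receives a single dose on Day 1, so nothing remains to be held. The period difference then affects only whether the rule leads to an SMC review and recommendation. Section 3.4 leads there, and 3.8 links early termination to triggered stopping rules. The synopsis, 3.1 and SAP 2.2 do not reach this case. Section 8.5 does, and it also gives the SMC ongoing review of safety data during the study.

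**Step 4. Does anything rank the statements?** Section 9.4.5 and Table 3 of the protocol both point to 3.4 for the stopping rules. Neither says that 3.4 overrides 8.5 or the synopsis.

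**Step 5. How likely is the trigger?** Assume independent participants with a constant SAE risk p. Then P(at least one SAE) = 1 − (1 − p)^n. The inputs are n = 12 (Cohort 1) and n = 23 (all randomized). For p, the documents offer only one SAE among 28 enrolled in the earlier Phase 1 IV study (protocol 1.2). That study was placebo-controlled, the arm of the SAE is not given, and the SAE was judged unrelated. It is used here as a rough guide.

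| Assumed p | n = 12 | n = 23 |
|---|---|---|
| 1% | 1 − 0.99^12 = 11% | 1 − 0.99^23 = 21% |
| 1/28 = 3.6% | 1 − (27/28)^12 = 35% | 1 − (27/28)^23 = 57% |
| 5% | 1 − 0.95^12 = 46% | 1 − 0.95^23 = 69% |

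The exact 95% interval for 1/28 runs from 0.09% to 18.3%, which gives 1% to 91% for n = 12 and 2% to 99% for n = 23. The input is therefore weak. These are also probabilities over full follow-up. The chance of an SAE while someone is still waiting to be dosed is lower.

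**The case against.** The strongest reply is that the statements form layers: the PI or medical monitor may pause at once, and the Sponsor then holds pending SMC review. A Sponsor hold breaches none of the optional versions, 3.4 and 8.5 both commit to SMC review, and two cross-references name 3.4 as the home of the stopping rules. The medical monitor is the sponsor's own (protocol 6.2 and 8.1.9), so a pause by that person is arguably a sponsor action. Procedures are also deferred to the SMC Charter, which is not among the documents.

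Part of this stands. The conflict is between required and optional, not between two incompatible commands, and the difference in actor is sharpest where the PI decides. The layered reading still fails as a full answer. The triggers and the action are identical, no section describes an escalation, and if the Sponsor must hold every time, the discretion in 8.5 has nothing left to decide. The charter may show what was done in practice, but it cannot remove a contradiction inside the protocol.

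A reader might also infer several stronger points that the documents do not support:

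- **A conflict over causality.** Section 3.4 opens with "The following related safety stopping rules apply throughout the entire study", and 8.5 counts an SAE whatever its relationship to the product. In 3.4, however, the word follows a sentence on the sentinel safety review and most naturally refers to that review. The SAE trigger itself carries no causality limit, so the two agree.
- **A conflict over grades.** Section 4.3.2 says "the injection(s) can be stopped if Grade 2 or higher or serious AE". It governs one participant's injection, not a pause of the study, and may use a different threshold.
- **No safeguard after enrolment.** This would follow only if the synopsis, 3.1 or SAP 2.2 were read alone; 3.4 and 8.5 both continue.
- **Up to 56 days of uncovered follow-up as a measure of size.** With single dosing there is nothing left to hold in that time.
- **Failure of the main safeguard.** The protocol also has staggered dosing, SMC review of the 12 Cohort 1 participants before Cohort 2, overnight observation and injection-level stopping.

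**Conclusion.** The inconsistency is real and narrow. For identical triggers the protocol makes the pause mandatory in one section and optional in three other places, and it differs on who imposes it. SAP 2.2 adds a third combination. The period also differs, but this is secondary: it bears mainly on whether a late event leads to SMC review under this rule, and 8.5 already provides ongoing SMC review.

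The point changes no estimate or confidence interval. It matters because this is an operative safety rule, and compliance with it cannot be judged while its statements disagree. A single SAE is a plausible trigger (21% to 69% among 23 participants for assumed risks of 1% to 5%), but that range rests on an assumed risk and on full follow-up. The documents do not say whether any triggering event occurred in this study, so no breach can be inferred.

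**What to change.** Reconcile the synopsis and protocol 3.1, 3.4 and 8.5 into one statement that says whether the hold is mandatory, who imposes it and over what period. Replace the other statements with a cross-reference to it, and align the summary in SAP 2.2 and the SMC Charter. Which version applies is for the sponsor and the SMC to decide.

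The SAP reports in the past tense that 23 participants were enrolled, so new wording cannot change how dosing was conducted. Its remaining use is in the study report: assess any triggering event against the single agreed rule, and disclose that the protocol carried differing statements when the event occurred.

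The cost is wording in two documents and a check against the charter. No data collection or analysis changes.
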